5. STUDY PROCEDURES

5.1. Subject enrollment

Potential subjects will be identified from the patients presenting at the clinic. Additionally, a flyer will be placed in the check-in area and/or the in-house TV's of the different locations, on the practices website and social media as deem necessary. Once identified as a study candidate, the patient will be asked if he/she would like to participate. The sub-investigator(s), study coordinator or an appropriately trained staff member will answer any and all questions and will obtain informed consent. A copy of the informed consent document will be given to the subject. The principal investigator

will be available if the subject wants to discuss further details with him. Any testing that is part of the investigative site's standard preoperative cataract evaluation may be performed prior to the patient given consent, provided these tests are conducted within 90 days of surgery. The patient will understand that participation in the study, or declining to participate, will not affect his/her quality of care.

No subject will be enrolled into the study that does not meet the inclusion/exclusion criteria and does not consent to be enrolled in the study. Informed consent will be obtained prior to collecting any data for the study. The original documents will be maintained by the investigator as a permanent part of the subject's research records and a copy will be provided to the patient.

5.2. Informed consent:

Subjects will be consented either in person in the office or verbally over the phone.

- In person consent process: Patients being considered for enrollment who are consented in the office will be required to sign the ICF agreeing to participate in the study. A copy of the signed consent form will be given to the subject.
- Over the phone consent process: Site staff delegated to perform the informed consent process along with a witness will sign the ICF. Subject will be asked to sign the consent during visit 2. A copy of the signed consent form will be given to the subject.

5.3. Surgery Procedures:

Subjects will be implanted with the Symphony with IntelliLight in the dominant eye and a Synergy lens in the non-dominant eye. Patients will receive either a non-toric or toric IOL based on the amount of astigmatism. The target refraction for both eyes will be closest to plano.

5.4. Study Visit Schedule and Assessments (Table 1).

5.4.1. Visit Schedule: Subjects will be examined at the following intervals:

1. Visit 1: Screening and enrollment: Preoperative evaluation completed not more than eight weeks before surgery
2. Visit 2: Day of Surgery for each eye
3. Visit 3: Month 3: 90 ±15 days postoperative after second eye surgery

5.4.2. Measurements and evaluations

1. Visit 1: Informed consent process will be conducted at this visit. Assessments include best-corrected Snellen visual acuity, intraocular pressure (IOP), slit lamp examination including dilated fundus exam, cataract density and type, and visual symptoms, patient satisfaction, spectacle independence and visual function

questionnaires. Any testing that is part of the site’s preoperative cataract surgery standard of care evaluation may be performed prior to signing the informed consent provided these tests are conducted within 90 days of the surgery and notation of the date performed is entered onto the CRF. The surgeon’s standard pre-cataract surgery treatment will be used in all patients

2. Visit 2: The surgeon may use his preferred cataract extraction technique (manual or laser). The lens will be implanted in the bag. The following information will be captured the day of surgery: phaco technique (manual or laser), lens implanted and power, target refraction, residual astigmatism and axis for Toric Calculator (if applicable), additional surgical procedures, intraoperative complications, and any device deficiencies. The surgeon’s standard post cataract surgery treatment will be used in all patients.

Visit 3: Slit lamp examination, manifest refraction, monocular and binocular uncorrected as well as distance corrected visual acuities will be evaluated at 4 m, 66 cm, 40 cm, 33 cm and best distance, and defocus curve. Additionally, dilated fundus exam (as deemed necessary by the investigator), visual symptoms, patient satisfaction, spectacle independence and visual function questionnaires, adverse events and any device deficiencies will be evaluated.

Table 1. Study Visit Schedule and Assessments

| | Visit 1 Screening | Visit 2 and 2A DOS | Visit 3 3-Month 90 ±15 days |
|--------------------------------|----------------------|-----------------------|-----------------------------------|
| Informed Consent | X | | |
| Inclusion/Exclusion | X | X | |
| Demographics/Ocular history | X | | |
| BCVA Snellen | X | | |
| Eye dominance | X | | |
| UCVA ETDRS (4m) | | | X* |
| UCIVA ETDRS (66 cm) | | | X* |
| UCNVA ETDRS (40 cm) | | | X* |
| UCNVA ETDRS (33 cm) | | | X* |
| UCNVA ETDRS (at best distance) | | | X* |
| Manifest refraction – Max Plus | | | X |
| BCVA ETDRS (4m) | | | X* |
| DCIVA ETDRS (66 cm) | | | X* |

| | | | |
|--------------------------------|---|---|-----|
| DCNVA ETDRS (40 cm) | | | X* |
| DCNVA ETDRS (33 cm) | | | X* |
| DCNVA ETDRS (at best distance) | | | X* |
| Defocus curve | | | X** |
| SLE | X | | X |
| Intraocular pressure | X | | |
| Dilated fundus exam | X | | X† |
| Cataract density / type | X | | |
| Intraoperative data | | X | |
| Toric IOL position | | X | X† |
| Questionnaires | X | | X |
| AE/Device deficiencies | | X | X |

X To be performed as scheduled

* Monocular and binocular testing

** Binocular testing only

†To be performed as deem necessary by the investigator.

DC: distance corrected.

5.5. Study endpoint criteria

5.5.1. Patient Completion of Study: If a study patient has completed the final visit (Visit 3) of the study, he/she is considered to have completed the study.

5.5.2. Patient Discontinuation: Each study patient may voluntarily discontinue the study at any time they choose. Study patients who cannot complete the study for administrative reasons (e.g., non-compliance, failure to meet visit schedule, etc.) will be discontinued from the study. Study patients discontinued during the enrollment phase (prior to surgery) of the study will be replaced. Subjects who are discontinued after first eye surgery before second eye surgery will also be replaced.

5.5.3. Patient Termination: A study patient will be terminated if the study patient develops any severe adverse event that may be related to the study. A study patient will receive appropriate treatment at the discretion of the investigator. Notification of termination will be clearly documented. These study patients are considered to have completed the study and will not be replaced.

5.5.4. Study Termination: The investigator with appropriate notification may terminate the study. If, after clinical observations, the investigator feels that it may be unwise to continue the study, he may stop the study.

5.5.5. Study Completion: The study will be complete when all enrolled patients have completed Visit 3 or have been terminated from the study.

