4. INCLUSION/EXCLUSION CRITERIA

4.1. Inclusion Criteria:

Subjects **MUST** fulfill the following conditions to qualify for enrollment into the trial

1. Subject is undergoing bilateral lens extraction with intraocular lens implantation of the Symphony with InteliLight in the dominant eye and a Synergy in the non-dominant eye.
2. Gender: Males and Females.
3. Age: 50 years and older.
4. Willing and able to provide written informed consent for participation in the study
5. Willing and able to comply with scheduled visits and other study procedures.
6. Scheduled to undergo standard cataract surgery with topical anesthesia in both eyes within 2 to 30 days between surgeries
7. Subjects who require an IOL power in the range of +5.00 D to +34.0 D only.
8. Subjects who require a toric IOL up to +3.75 D at the IOL plane (2.57 D corneal plane).
9. Potential postoperative visual acuity of 0.2 logMAR (20/32 Snellen) or better in both eyes.

4.2. Exclusion Criteria:

Subjects with **ANY** of the following conditions on the eligibility exam may **NOT** be enrolled into the trial.

1. Severe preoperative ocular pathology: amblyopia, rubella cataract, proliferative diabetic retinopathy, shallow anterior chamber, macular edema, retinal detachment, aniridia or iris atrophy, uveitis, history of iritis, iris neovascularization, medically uncontrolled glaucoma, microphthalmos or macrophthalmos, optic nerve atrophy, macular degeneration (with anticipated best postoperative visual acuity less than 20/30), advanced glaucomatous damage, etc.
2. Uncontrolled diabetes.
3. Use of any systemic or topical drug known to interfere with visual performance.
4. Contact lens use during the active treatment portion of the trial.
5. Any concurrent infectious/non-infectious conjunctivitis, keratitis or uveitis.
6. Clinically significant corneal dystrophy
7. History of chronic intraocular inflammation.
8. History of retinal detachment.
9. Pseudoexfoliation syndrome or any other condition that has the potential to weaken the zonules.
10. Previous intraocular surgery.
11. Previous corneal refractive surgery (i.e. LASIK, PRK, RK).
12. Previous keratoplasty
13. Severe dry eye
14. Pupil abnormalities
15. Anesthesia other than topical or peribulbar anesthesia (i.e. retrobulbar, general, etc).
16. Any clinically significant, serious or severe medical or psychiatric condition that may increase the risk associated with study participation or may interfere with the interpretation of study results.

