17. Participation in (or current participation) any ophthalmic investigational drug or ophthalmic device trial within the previous 30 days prior to the start date of this trial.

The principal investigator reserves the right to declare a patient ineligible or non-evaluable based on medical evidence that indicates the patient is unsuitable for the trial.

4.3. Exclusion Criteria at time of surgery:

If any of the following exclusion criteria are applicable to the study eye, the subject should not continue in the study.

1. Other ocular surgery procedures, i.e. iStent, anterior vitrectomy
2. Significant vitreous loss
3. Significant anterior chamber hyphema
4. Uncontrollable intraocular pressure
5. Zonular or capsular rupture

6. Bag-sulcus, sulcus-sulcus or unknown placement of the haptics
7. Suturing of incision required at time of surgery
8. Intraocular lens tilt or decentration
9. Significant sedation or retrobulbar block during surgery
10. Other procedure, such as pupil stretch, expanders, iris hooks during surgery

Note: Any subject in which surgery has been aborted for either eye should immediately be discontinued from the study and an exit form completed for that subject. These subjects will be followed up as per the clinic standard of care, monitored for safety, and their data will be excluded from the study efficacy analysis (obtained from FDA Database Research Results Feb, 05, 2009). All adverse events will be appropriately documented and reported.

Additionally, participants who are considered to be a vulnerable subject population are not to be enrolled into the study without prior written authorization from both the Sponsor and the IRB to ensure that a description of additional safeguards are in place during the consenting and enrollment processes. Vulnerable populations include, but are not limited to, the following:

1. Prisoners
2. Nursing home residents /institutionalized individuals
3. Mentally disabled /cognitively impaired individuals
4. Sponsor employees and their family members
5. Site employees and their family members that are directly and indirectly involved with the study
6. Students of the university or the principal investigator participating in the study
7. Economically and/or educationally disadvantaged individuals
8. Comatose individuals / traumatized individuals
9. Adults who do not read and/or write
10. Hearing impaired individuals
11. Terminally ill individuals / individuals with life-threatening conditions

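### Section 5.5.3 counts subjects terminated for a possibly related severe adverse event as having completed the study, without asking for the Visit 3 data that carry the primary endpoint

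*Combined protocol and SAP*

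**What the plan says.** Section 5.5 of the combined protocol and SAP sets out how a subject leaves the study.

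- 5.5.1 (completion): "If a study patient has completed the final visit (Visit 3) of the study, he/she is considered to have completed the study".
- 5.5.2 (discontinuation) covers voluntary and administrative exits. It replaces subjects lost before surgery and adds: "Subjects who are discontinued after first eye surgery before second eye surgery will also be replaced".
- 5.5.3 (termination): "A study patient will be terminated if the study patient develops any severe adverse event that may be related to the study". On their status: "These study patients are considered to have completed the study and will not be replaced".
- 5.5.5 (end of study): "The study will be complete when all enrolled patients have completed Visit 3 or have been terminated from the study".

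The note in Section 4.3 also uses the word 'discontinued', this time for a surgical event: "Any subject in which surgery has been aborted for either eye should immediately be discontinued from the study". It asks for an exit form and safety monitoring and excludes these subjects from the efficacy analysis. No equivalent rule on data or analysis is given for subjects terminated under 5.5.3.

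Sections 5.4.1 and 5.4.2 and Table 1 schedule one visit after the days of surgery, Visit 3, at 90 ±15 days after the second eye. The defocus curve and the postoperative questionnaires appear only there.

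**The concern.** The same word, 'completed', describes a subject with the full 3-month assessment and a subject who may have none of it. Someone following 5.5.3 has no instruction to bring a terminated subject back for Visit 3, and the label suggests that nothing is outstanding.

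These subjects would be lost because of a severe event that may be related to the study, so their absence is plausibly informative. The outcomes compared with the historical Synergy OU group (satisfaction, spectacle independence and visual symptoms) are ones that such an event could well affect. Section 6 has no missing-data rule and no defined analysis population, so nothing later in the plan makes up for the gap.

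A second, narrower question is replacement. A subject who has received the first lens and leaves before the second because of such an event can come under both 5.5.2 (replaced) and 5.5.3 (not replaced).

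**Working it through.** **The plan's own figure.** Section 6.1 plans 40 enrolled subjects, supported only by a rule of thumb of at least 30. It gives no standard deviation, power or dropout rate, so 40 cannot be reproduced by formula. It exceeds 30 by 10.

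**Is Visit 3 needed to be 'completed'?**

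| Section | Status | Visit 3 needed? |
|---|---|---|
| 5.5.1 | completed | yes |
| 5.5.3 | terminated, counted as completed | not mentioned |
| 5.5.5 | Visit 3 done, or terminated | listed as alternatives |

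Section 5.5.5 confirms that termination does not presuppose Visit 3.

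**How long is a subject exposed to this?** Inclusion criterion 6 in Section 4.1 has surgery "in both eyes within 2 to 30 days between surgeries". Visit 3 falls 75 to 105 days after the second eye. From first lens to Visit 3:

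- shortest: 2 + 75 = 77 days
- longest: 30 + 105 = 135 days

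A termination at any time in this period, before Visit 3, leaves no 3-month data.

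**Effect on a completion count.** With one subject terminated before Visit 3 and 40 as the denominator, 40/40 = 100% are labelled complete, but 39/40 = 97.5% have Visit 3. The difference is 1/40 = 2.5 percentage points per subject.

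**Effect on precision.** The standard error grows by √(40/39) = 1.013, or 1.3%, for one lost subject. The half-width of a 95% confidence interval for a mean, t(0.975, n−1)/√n in standard deviation units, is:

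| n with Visit 3 | Half-width |
|---|---|
| 40 | 0.320 |
| 39 | 0.324 |
| 38 | 0.329 |
| 36 | 0.338 |
| 30 | 0.373 |

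More than 10 subjects would have to be lost to fall below 30.

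**Chance that the situation arises.** The documents give no event rate. For an assumed per-subject termination rate p, the chance of at least one in 40 is 1 − (1 − p)^40:

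| Assumed p | At least one of 40 |
|---|---|
| 1% | 33.1% |
| 2% | 55.4% |
| 5% | 87.1% |
| 10% | 98.5% |

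These are illustrations, not estimates.

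**Replacement overlap.** Suppose one subject leaves for such an event between the surgeries, and take 40 as the target for bilaterally implanted subjects (an assumption, since 6.1 speaks of enrolment). Other losses are ignored.

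| Rule applied | Enrolled | Can have Visit 3 |
|---|---|---|
| 5.5.2, replaced | 41 | 40 |
| 5.5.3, not replaced | 40 | 39 |

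No passage says which row applies.

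**The case against.** **The completion wording is not a strict contradiction.** Section 5.5.1 says 'if', not 'only if'. Section 5.5.3 can be read as a second administrative route to the same status, and 5.5.5 matches that reading. This stands as logic. It does not remove the practical point: the label covers subjects with and without the primary endpoint, and nothing asks for the missing visit.

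**No planned analysis uses the label.** Section 6 defines no completer population and no completion rate. This also stands. The 2.5 points apply only to a completion figure that someone chooses to report; the substantive loss is the Visit 3 data.

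**Not every terminated subject lacks data.** Table 1 schedules adverse event assessment on surgery days and at Visit 3. An event first found at Visit 3 can occur in a subject with complete data, so the point is confined to termination before Visit 3. Nor does 5.5.3 forbid a later Visit 3; it simply does not ask for one. The safety record is better provided for, since the Section 4.3 note says "All adverse events will be appropriately documented and reported".

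**A reader might infer that 5.5.2 and 5.5.3 flatly conflict on replacement.** The documents do not support that. The two sections stand under separate headings, and 5.5.3 can be read as the specific rule for severe events. What remains is an unresolved overlap: the replacement sentence in 5.5.2 names no reason for exit, and the Section 4.3 note shows that 'discontinued' is not limited to voluntary or administrative exits. An aborted first-eye operation is a poor illustration, because it is neither clearly before surgery nor clearly after first-eye surgery. A severe event between two otherwise uneventful operations raises the question more cleanly.

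**A reader might also infer that 5.5.5 leaves the study open whenever a subject discontinues.** That requires reading 'terminated' narrowly there while reading 'discontinued' broadly in 5.5.2. It is a clerical matter at most and forms no part of this point.

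**Conclusion.** The point holds as a cheap improvement. As written, a subject terminated under 5.5.3 before Visit 3 supplies no primary endpoint and no data for the historical comparison, and is still counted as having completed the study.

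The effect on precision is negligible. The size and direction of any bias are unknown and may be small, because the documents give neither the number nor the timing of such events. That the missing data are informative is plausible from the reason for exit; it is not shown.

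It would go too far to conclude that the 3-month results must be biased, or that they would contain no subject with such an event. It would also be wrong to use the share of follow-up time that lies between the surgeries as a measure of how often the replacement overlap would arise: calendar time is not risk.

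The criterion for terminating a subject is not questioned here, and no view is taken on which replacement rule is right.

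**What to change.** 1. In 5.5.1 and 5.5.3, reserve 'completed' for subjects who complete Visit 3.
2. Report subjects terminated under 5.5.3 as a separate category, 'terminated due to an adverse event'. Do not call them 'discontinued', since that word triggers replacement under 5.5.2 between surgeries and would settle item 4 by accident.
3. If such a subject has both study lenses and has not withdrawn consent, still seek the Visit 3 assessments and questionnaires, and include them in the 3-month results.
4. Reconcile 5.5.2, 5.5.3 and the Section 4.3 note so that one stated rule governs replacement after an exit between the two surgeries. The sponsor should choose the rule.

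The cost is a few sentences of amended text, minor follow-up effort for any terminated subject, and a slightly less favourable completion count. Visit 3 is already scheduled, so no new assessment is needed.

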6. STATISTICAL CONSIDERATIONS

6.1. Sample size

A total of 40 subjects will be enrolled. In order to calculate the sample size, we need to know an accurate estimate of the standard deviation of the outcome measure which we do not know; therefore, we consider this study a pilot trial. When estimating the sample size for a pilot study, the simplest method is to apply a sample size rule of thumb.

Browne suggests a general flat rule to 'use at least 30 subjects or greater to estimate a parameter'.

6.2. Statistical Analysis

All data will be collected by the site and entered into a database. Subjects will be assigned an ID number. Data analysis will be performed without patient identification. Statistical analysis will be performed using standard descriptive statistics and other tests as deemed appropriate based on the characteristics of the data to be analyzed. All statistical tests will be two-sided and interpreted at a 5% significance level. Vision satisfaction, spectacle independence and visual symptoms will be compared to a historical control of patients implanted bilaterally with Synergy OU. Data analysis will be conducted by a third-party consultant.

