Early reports from many centers across the country and other countries appear to indicate that the Synergy IOL implanted bilaterally is yielding very good results at all ranges, particularly at near.²⁻⁴ Anecdotally, some surgeons have reported excellent near vision with good but not great distance vision.

Prior to utilizing the Synergy IOL, our center along with many high-volume centers across the country, employed a mix and match strategy utilizing the TECNIS Symphony in the dominant eye and the TECNIS Multifocal in the non-dominant eye with good results and high patient satisfaction.⁵

We propose conducting a prospective evaluation of a mix and match strategy incorporating Symphony with InteliLight in the dominant eye and Synergy IOL in the non-dominant eye. The Symphony lens, an Extended Depth of Focus (EDOF) lens, known for its superior distance and intermediate vision, has been upgraded to the OptiBlue version (InteliLight). The Symphony with InteliLight has an enhanced echelette design and a violet light filter. The upgraded echelette design utilizes a high-resolution lathing process that helps reduce light scatter and halo intensity. The violet light filter is designed to mitigate halo, glare, and starbursts.

1. OBJECTIVE:

The purpose of this study is to evaluate the visual outcomes, visual disturbances, patient satisfaction and spectacle independence of the Symphony with InteliLight when implanted in

the dominant eye and a Synergy is implanted in the non-dominant eye in patients with or without astigmatism after routine cataract surgery.

2. STUDY ENDPOINTS:

1. Primary Endpoints:

Binocular defocus curve at 3 months

2. Secondary Endpoints:

- a. Monocular and binocular uncorrected and distance-corrected near at 40 cm visual acuity at 3 months.
- b. Monocular and binocular uncorrected and distance-corrected near at 33 cm visual acuity at 3 months
- c. Monocular and binocular uncorrected and distance-corrected intermediate (66 cm) visual acuity at 3 months
- d. Monocular and binocular uncorrected and best-corrected distance (4 m) visual acuity at 3 months
- e. To evaluate patient's vision satisfaction at 3 months
- f. To evaluate patient's spectacle independence at 3 months
- g. To evaluate visual symptoms using a questionnaire at 3 months
- h. To evaluate functional vision using a questionnaire at 3 months

3. STUDY DESIGN:

Prospective, multicenter (up to 2 site in US), non-randomized, bilateral eye study.

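### Is the primary defocus curve too loosely defined to give a fixed descriptive result?

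*Combined protocol and SAP*

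**What the plan says.** Section 2 names one primary endpoint, "Binocular defocus curve at 3 months". The secondary acuity endpoints are fuller: item a, for example, reads "Monocular and binocular uncorrected and distance-corrected near at 40 cm visual acuity at 3 months", which gives eye, correction state and distance.

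For Visit 3, Section 5.4.2 puts the test at the end of a list of acuities: "4 m, 66 cm, 40 cm, 33 cm and best distance, and defocus curve". Table 1 marks it at the 3-month visit with the footnote "Binocular testing only". Section 5.4.1 sets that visit at 90 ±15 days after the second eye.

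Section 6.1 calls the study a pilot because it would need "an accurate estimate of the standard deviation of the outcome measure which we do not know". It takes 40 subjects by a rule of thumb, "use at least 30 subjects or greater to estimate a parameter". Section 6.2 applies "standard descriptive statistics and other tests as deemed appropriate based on the characteristics of the data to be analyzed" to all data. The one comparison it names, with a historical bilateral Synergy group, covers three questionnaire outcomes and not the curve. Section 3 describes the design as "Prospective, multicenter (up to 2 site in US), non-randomized, bilateral eye study".

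**The concern.** A defocus curve is a set of acuities, one per lens level, not a single number. To reproduce the primary result exactly, a reader would need the range and step of the lenses, whether testing is done uncorrected or through the distance correction, and the quantity taken from the curve. That quantity could be a mean logMAR at each level, a dioptric range at some threshold, or an area. The documents state none of these. The correction state cannot safely be inferred, because Section 5.4.2 lists the curve after both uncorrected and distance-corrected acuities and its Table 1 row carries no prefix for either.

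Two things would be at stake. If two sites tested differently, their curves could not be pooled without assumptions. And if the summary were chosen after the curves had been seen, the most flattering one could be reported.

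**Working it through.** **The plan's own figure.** The sample size is 40 against a rule of at least 30, so the rule is met. It would still be met after a 25% loss: 40 × (1 − 0.25) = 30. The 25% is solved backwards and is not in the documents. With no SD, effect size or precision target stated, there is no power or precision figure to reproduce.

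**Precision of a per-level mean.** Half-width of the 95% CI in SD units = t(0.975, n − 1)/√n.

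- n = 40: 0.320
- n = 30: 0.373

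The documents give no SD. Assuming 0.08 to 0.15 logMAR, the half-width at n = 40 is 0.320 × 0.08 = 0.026 to 0.320 × 0.15 = 0.048 logMAR.

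**Which open items could be settled after seeing the data?**

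| Item | Set when | Open to the analyst afterwards? |
|---|---|---|
| Defocus range and step | At testing | No |
| Correction state | At testing | No |
| Summary measure, threshold, interpolation | At analysis | Yes |

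The first two rows therefore bear only on consistency between sites, and only if a second site is used.

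**Size of a correction-state difference.** Assume a mean residual refraction of 0.25 D and a curve slope of 0.1 to 0.4 logMAR per D. Neither is in the documents, and Section 5.3 aims both eyes at plano. The shift is 0.25 × 0.1 = 0.025 to 0.25 × 0.4 = 0.10 logMAR, and zero where the curve is flat. Against the half-width, that is 0.025/0.048 = 0.5 to 0.10/0.026 = 3.9.

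**Size of a threshold choice.** Suppose the summary were the dioptric range at a threshold, and the threshold moved from 0.2 to 0.3 logMAR. On a locally linear curve:

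- shift in D = 0.1/slope
- SD in D = (logMAR SD)/slope
- ratio of shift to half-width = (0.1/slope) / (0.320 × SD/slope) = 0.1/(0.320 × SD)

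The slope cancels. With SD 0.15 the ratio is 0.1/0.048 = 2.1; with SD 0.08 it is 0.1/0.0256 = 3.9. Letting slope and dioptric SD vary independently would give a wider span, 1.0 to 7.8, but its ends are inconsistent with the assumed logMAR SDs. The 7.8 pairs slope 0.1 with 0.4 D, implying 0.1 × 0.4 = 0.04 logMAR. The 1.0 pairs slope 0.4 with 0.8 D, implying 0.4 × 0.8 = 0.32 logMAR. Both lie outside 0.08 to 0.15.

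**What the ratio means.** Ranges at 0.2 and at 0.3 logMAR are two different quantities. Their difference is not an error in either, and the protocol proposes no threshold.

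**What the generic sentence yields for this endpoint.** Descriptive statistics applied to acuities recorded at a series of levels give a mean (or median) and spread at each level, which is the curve itself. Writing out a definition of the primary parameter would arrive at the same place.

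**The case for a change.** The strongest opposing case is that a descriptive result still needs a stated quantity. The protocol shows in secondary endpoints a to d that it can be specific. A third-party consultant will do the analysis and up to two sites will test, so local habit is a weak substitute for text. Section 6.2 ties the method to the characteristics of the data, which on its face allows a choice after the fact. Writing the definition down would cost a few sentences.

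Much of this stands as description. The details are absent, and a careful author would have included them. Less of it stands as a defect. The secondary acuities rely on the same generic sentence for their summary statistic, so that gap is not peculiar to the primary. The lens levels have to be recorded to produce a curve at all. Section 8 requires examinations to be entered on case report forms, which are not among the documents and may well fix the levels for both sites. Nor does the study fail a stated aim of estimating one parameter: that phrase appears only inside the cited sample-size rule, while the objective in Section 1 is a broad evaluation of visual outcomes and patient reports.

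**Conclusion.** The concern is accurate about what is missing, but it does not call for a change. The plan fixes the eye condition (binocular) and the time (3 months, 90 ±15 days). It leaves to ordinary practice the levels, the correction state and the summary. In a single-arm pilot with no hypothesis, comparison or decision rule attached to the curve, the natural reading is a per-level summary, and that gives a usable primary result.

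The sizes above, 0.5 to 3.9 half-widths for correction state and 2.1 to 3.9 for a threshold change, rest wholly on assumed SDs, slopes and residual refraction, with all 40 subjects evaluable. They show that different definitions give different numbers, not that the plan as written would give a wrong one. The judgement would differ if the protocol drew a comparative claim from the curve or set a success threshold on it; it does neither. This is a gap in detail that the sites and analyst can be expected to fill sensibly.
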